SOURCE: USERNAME\SPONSOR\PROJECT\JOBNAME (DATE, TIME)

Listing 16.2.6.3.1: RosaQoL Descriptions
(Page xx of yy)

Number	RosaQoL Question
17	My skin flushes
18	My skin gets irritated easily (cosmetics, aftershaves, cleansers)
19	My eyes bother me (feels dry or gritty)
20	I think about my rosacea
21	I avoid certain environments (heat, humidity, cold) because of my rosacea

SOURCE: USERNAME\SPONSOR\PROJECT\JOBNAME (DATE, TIME)

Listing 16.2.6.3.2: RosaQoL
Treatment Arm
(Page xx of yy)

Subject	Age/Sex	Eval	Visit	Date of Assessment	1	2	3	4	5	6	7	8	9	10	11	12	13	14	15	16	17	18	19	20	21
xxxxxx	xxxxx	xxxxxxxx	xxxxxxxxxx	xxxxxxxxxx	x	x	x	x	x	x	x	x	x	x	x	x	x	x	x	x	x	x	x	x	x
			xxxxxxxxxx	xxxxxxxxxx	x	x	x	x	x	x	x	x	x	x	x	x	x	x	x	x	x	x	x	x	x
xxxxxx	xxxxx	xxxxxxxx	xxxxxxxxxx	xxxxxxxxxx	x	x	x	x	x	x	x	x	x	x	x	x	x	x	x	x	x	x	x	x	x
			xxxxxxxxxx	xxxxxxxxxx	x	x	x	x	x	x	x	x	x	x	x	x	x	x	x	x	x	x	x	x	x
xxxxxx	xxxxx	xxxxxxxx	xxxxxxxxxx	xxxxxxxxxx	x	x	x	x	x	x	x	x	x	x	x	x	x	x	x	x	x	x	x	x	x
			xxxxxxxxxx	xxxxxxxxxx	x	x	x	x	x	x	x	x	x	x	x	x	x	x	x	x	x	x	x	x	x
xxxxxx	xxxxx	xxxxxxxx	xxxxxxxxxx	xxxxxxxxxx	x	x	x	x	x	x	x	x	x	x	x	x	x	x	x	x	x	x	x	x	x
			xxxxxxxxxx	xxxxxxxxxx	x	x	x	x	x	x	x	x	x	x	x	x	x	x	x	x	x	x	x	x	x

1 = Never; 2 = Rarely; 3 = Sometimes; 4 = Often; 5 = All the time; ND = Not Done

SOURCE: USERNAME\SPONSOR\PROJECT\JOBNAME (DATE, TIME)

Listing sorted by Subject and Visit Number

Listing 16.2.6.3.3: RosaQoL Subscales Scores
Treatment Arm
(Page xx of yy)

Subject	Age/Sex	Eval	Visit	Date of Assessment	Total Score	Symptom	Functional	Emotion
xxxxxx	xxxxx	xxxxxxxx	xxxxxxxx	xxxxxxxx	xx	xx	xx	xx
			xxxxxxxx	xxxxxxxx	xx	xx	xx	xx
xxxxxx	xxxxx	xxxxxxxx	xxxxxxxx	xxxxxxxx	xx	xx	xx	xx
			xxxxxxxx	xxxxxxxx	xx	xx	xx	xx
xxxxxx	xxxxx	xxxxxxxx	xxxxxxxx	xxxxxxxx	xx	xx	xx	xx
			xxxxxxxx	xxxxxxxx	xx	xx	xx	xx
xxxxxx	xxxxx	xxxxxxxx	xxxxxxxx	xxxxxxxx	xx	xx	xx	xx
			xxxxxxxx	xxxxxxxx	xx	xx	xx	xx
xxxxxx	xxxxx	xxxxxxxx	xxxxxxxx	xxxxxxxx	xx	xx	xx	xx
			xxxxxxxx	xxxxxxxx	xx	xx	xx	xx
xxxxxx	xxxxx	xxxxxxxx	xxxxxxxx	xxxxxxxx	xx	xx	xx	xx
			xxxxxxxx	xxxxxxxx	xx	xx	xx	xx

SOURCE: USERNAME\SPONSOR\PROJECT\JOBNAME (DATE, TIME)

Listing sorted by Subject and Visit Number

Listing 16.2.6.4: Erythema Severity/Telangiectasia Assessments
 Treatment Arm
 (Page xx of yy)

Subject	Age/Sex	Eval	Visit	Date of Assessment	Evaluator Initials	Assessment	Result
xxxxxx	xxxx	xxxxxxxx	xxxxxxxx	xxxxxxxx	xxx	Rosacea Erythema Telangiectasia	xxxxxxxx xxxxxxxx
			xxxx x	xxxxxxxx	xxx	Rosacea Erythema Telangiectasia	xxxxxxxx xxxxxxxx
			xxxx x	xxxxxxxx	xxx	Rosacea Erythema Telangiectasia	xxxxxxxx xxxxxxxx
			xxxx x	xxxxxxxx	xxx	Rosacea Erythema Telangiectasia	xxxxxxxx xxxxxxxx
			xxxx xxxxx	xxxxxxxx	xxx	Rosacea Erythema Telangiectasia	xxxxxxxx xxxxxxxx
xxxxxx	xxxx	xxxxxxxx	xxxxxxxx	xxxxxxxx	xxx	Rosacea Erythema Telangiectasia	xxxxxxxx xxxxxxxx
			xxxx x	xxxxxxxx	xxx	Rosacea Erythema Telangiectasia	xxxxxxxx xxxxxxxx
			xxxx x	xxxxxxxx	xxx	Rosacea Erythema Telangiectasia	xxxxxxxx xxxxxxxx
			xxxx x	xxxxxxxx	xxx	Rosacea Erythema Telangiectasia	xxxxxxxx xxxxxxxx
			xxxx xxxxx	xxxxxxxx	xxx	Rosacea Erythema Telangiectasia	xxxxxxxx xxxxxxxx

SOURCE: USERNAME\SPONSOR\PROJECT\JOBNAME (DATE, TIME)

Listing sorted by Subject and Visit Number, and Assessment (in order presented on eCRF).

Listing 16.2.6.5: PRO - PAPSS, PAPI, PGI-S
 Treatment Arm
 (Page xx of yy)

Subject	Age/Sex	Eval	Visit	Date of Assessment	PRO Category	Object of Assessment	Result
xxxxxx	xxxx	xxxxxxxx	xxxxxxxx	xxxxxxxx	PAPSS	BURNING	xxxxxxxx
						ITCHING	xxxxxxxx
						REDNESS	xxxxxxxx
						BUMPS	xxxxxxxx
					PAPI	EMBARRASSED	xxxxxxxx
						SELF-CONSCIOUS	xxxxxxxx
						FRUSTRATED	xxxxxxxx
					PGI-S	ROSACEA	xxxxxxxx
			xxxx x	xxxxxxxx	PAPSS	BURNING	xxxxxxxx
						ITCHING	xxxxxxxx
						REDNESS	xxxxxxxx
						BUMPS	xxxxxxxx
					PAPI	EMBARRASSED	xxxxxxxx
						SELF-CONSCIOUS	xxxxxxxx
						FRUSTRATED	xxxxxxxx
					PGI-S	ROSACEA	xxxxxxxx

SOURCE: USERNAME\SPONSOR\PROJECT\JOBNAME (DATE, TIME)

Listing sorted by Subject and Visit Number, PRO Category, and Assessment (in order presented on eCRF).

Listing 16.2.6.6: PRO - PGI-C, PGI-TS, PGI-SE
Treatment Arm
(Page xx of yy)

Subject	Age/Sex	Eval	Visit	Date of Assessment	PRO Category	Result
xxxxxx	xxxx	xxxxxxxx	xxxxxxxx	xxxxxxxx	PGI-C	xxxxxxxxxxxxxx
					PGI-TS	xxxxxx xxx xxx
					PGI-SE	xxxxxxxxxxxxxx
					PGI-C	xxxxxxxxxxxxxx
					PGI-TS	xxxxxx xxx xxx
					PGI-SE	xxxxxxxxxxxxxx
					PGI-C	xxxxxxxxxxxxxx
					PGI-TS	xxxxxx xxx xxx
					PGI-SE	xxxxxxxxxxxxxx
xxxxxx	xxxx	xxxxxxxx	xxxxxxxx	xxxxxxxx	PGI-C	xxxxxxxxxxxxxx
					PGI-TS	xxxxxx xxx xxx
					PGI-SE	xxxxxxxxxxxxxx
					PGI-C	xxxxxxxxxxxxxx
					PGI-TS	xxxxxx xxx xxx
					PGI-SE	xxxxxxxxxxxxxx

SOURCE: USERNAME\SPONSOR\PROJECT\JOBNAME (DATE, TIME)

Listing sorted by Subject, Visit Number, and PRO Assessment (in order presented on eCRF).

Listing 16.2.7.1: Cutaneous Safety and Tolerability Assessments
Treatment Arm
(Page xx of yy)

Subject	Age/Sex	Eval	Visit	Date of Assessment	Evaluator Initials	Test	Result
xxxxxx	xxxx	xxxxxxxx	xxxxxxxx	xxxxxxxx	xxx	Dryness Scaling Itching Burning/Stinging	xxxxxxx xxx xxxx xxxxxxxxxxxx xxxxxxxxxxxx
			xxxx x	xxxxxxxx	xxx	Dryness Scaling Itching Burning/Stinging	xxxxxxx xxx xxxx xxxxxxxxxxxx xxxxxxxxxxxx
			xxxx x	xxxxxxxx	xxx	Dryness Scaling Itching Burning/Stinging	xxxxxxx xxx xxxx xxxxxxxxxxxx xxxxxxxxxxxx
			xxxxxxxx	xxxxxxxx	xxx	Dryness Scaling Itching Burning/Stinging	xxxxxxx xxx xxxx xxxxxxxxxxxx xxxxxxxxxxxx
xxxxxx	xxxx	xxxxxxxx	xxxxxxxx	xxxxxxxx	xxx	Dryness Scaling Itching Burning/Stinging	xxxxxxx xxx xxxx xxxxxxxxxxxx xxxxxxxxxxxx
			xxxx x	xxxxxxxx	xxx	Dryness Scaling Itching Burning/Stinging	xxxxxxx xxx xxxx xxxxxxxxxxxx xxxxxxxxxxxx

SOURCE: USERNAME\SPONSOR\PROJECT\JOBNAME (DATE, TIME)

Listing sorted by Subject, Visit Number, and Test (in order presented on eCRF).

Listing 16.2.7.2.1: Unique Adverse Events Coded to MedDRA System Organ Classes and Preferred Terms
 Treatment Arm
 (Page xx of yy)

MedDRA System Organ Class	MedDRA Preferred Term	Application Area	Adverse Event
XXXXXXXXXXXXXXXXXXXX	XXXXXXXXXXXXXXXXXXXX	XX	XXXXXXXXXXXXXXXXXXXX
		XX	XXXXXXXX
		XX	XXXXX XXXXXXXX
	XXXXXXXXXX	XX	XXXXXXXXXX
XXXXXX XXXXXXXX XXXXXXXX	XXXXXXXXXX	XX	XXXXXXXXXX
XXXX XXXXXXXXXXXXXXX XXXXXXX XXXXXXXX	XXXXXXXXXX	XX	XXXXXXXXXXXX XX XXXXXXXX
	XXXX XXXXXXXXXXXXXXX	XX	XXXXXXXX XXXX XXXXXXXXXXXXXXX XXXX

Note: System Organ Class and Preferred Term map to MedDRA (Version 21.0).

SOURCE: USERNAME\SPONSOR\PROJECT\JOBNAME (DATE, TIME)

Listing sorted by System Organ Class, Preferred Term, Adverse Event.

Listing 16.2.7.2.2: Pre-Treatment Adverse Events
Treatment Arm
(Page xx of yy)

S: Subject	S: MedDRA System Organ Class	A: In the Application Area	A: Action Taken with Study Drug	S: Start Date (Day) ¹
A: Age/Sex	P: MedDRA Preferred Term	G: Severity	T: Action Taken to Treat Event	E: End Date (Day) ¹
E: Eval	A: Adverse Event	R: Relationship to Study Drug	O: Outcome	
		S: Serious Event		
S: xxxxxx	S: xxxx xxx xxxxxxxxxxxxxxx xxxxxx	A: xx	A: xxx xx xxxxxxxx	S: xxxxxxxxxxxxxxxx
A: xxxx	P: xxx xxxxxxxxxxxxxxx	G: xxxxx	T: xxxxx	E: xxxxxxxxxxxxxxxx
E: xxxxxxxx	A: xxxxxxxx xxx xxxxxxxxxxx xxxxx	R: xxx xxxxxxxx	O: xxxxxxxxxxxxxxxx	
		S: xx		
	S: xxxxxxxx xxxxxxxxxxx xxx xxxxxxxxxxx	A: xxx	A: xxx xxxxxxxxxxx	S: xxxxxxxxxxxxxxxx
	P: xxxxxxxxxxx	G: xxxxx	T: xxxxxxxxxxx xxxxxxxxxxx	E: xxxxxxxxxxxxxxxx
	A: xxxxxxxx xxxxx xxxxxxxxxxx xxxxx	R: xxx xxxxxxxx	O: xxxxxxxxxxxxxxxx	
		S: xx		
S: xxxxxx	S: xxxx xxxxxxxxxxx xxxxxx	A: xx	A: xxx xx xxxxxxxx	S: xxxxxxxxxxxxxxxx
A: xxxx	P: xxxxxxxxxxx	G: xxxxxxxx	T: xxxxx	E: xxxxxxxxxxxxxxxx
E: xxxxxxxx	A: xxxxxxxxxxx xxxxx	R: xxx xxxxxxxx	O: xxxxxxxxxxxxxxxx	
		S: xx		
S: xxxxxx	S: xxxx xxxxxxxxxxx xxxxxx	A: xx	A: xxx xx xxxxxxxx	S: xxxxxxxxxxxxxxxx
A: xxxx	P: xxxxxxxxxxx	G: xxxxxxxx	T: xxxxx	E: xxxxxxxxxxxxxxxx
E: xxxxxxxx	A: xxxxxxxxxxx xxxxx	R: xxxxxxxx	O: xxxxxxxxxxxxxxxx	
		S: xxx		
	S: xxxxxxxx xxxxxxxxxxx xxx xxxxxxxxxxx	A: xxx	A: xxx xxxxxxxxxxx	S: xxxxxxxxxxxxxxxx
	P: xxxxxxxxxxx	G: xxxxx	T: xxxxxxxxxxx xxxxxxxxxxx	E: xxxxxxxxxxxxxxxx
	A: xxxxxxxx xxxxx xxxxxxxxxxx xxxxx	R: xxx xxxxxxxx	O: xxxxxxxxxxxxxxxx	
		S: xx		

¹ Day is calculated as date - date of first application for dates prior to first application. Otherwise, day is calculated as date - date of first application + 1 for dates on or after first application.

Note: System Organ Class and Preferred Term map to MedDRA (Version 21.0).

SOURCE: USERNAME\SPONSOR\PROJECT\JOBNAME (DATE, TIME)

Listing sorted by Subject, Start Date, End Date, Adverse Event.

Listing 16.2.7.2.3: Treatment-Emergent Adverse Events
 Treatment Arm
 (Page xx of yy)

S: Subject	S: MedDRA System Organ Class	A: In the Application Area	A: Action Taken with Study Drug	S: Start Date (Day) ¹
A: Age/Sex	P: MedDRA Preferred Term	G: Severity	T: Action Taken to Treat Event	E: End Date (Day) ¹
E: Eval	A: Adverse Event	R: Relationship to Study Drug	O: Outcome	
		S: Serious Event		
S: xxxxxx	S: xxxx xxx xxxxxxxxxxxxxxx xxxxxx	A: xx	A: xxx xx xxxxxxxx	S: xxxxxxxxxxxxxxxx
A: xxxx	P: xxx xxxxxxxxxxxxxxx	G: xxxxx	T: xxxxx	E: xxxxxxxxxxxxxxxx
E: xxxxxxxx	A: xxxxxxxx xxx xxxxxxxxxxx xxxxx	R: xxx xxxxxxxx	O: xxxxxxxxxxxxxxxx	
		S: xx		
	S: xxxxxxxx xxxxxxxxxxx xxx xxxxxxxxxxx	A: xxx	A: xxx xxxxxxxxxxx	S: xxxxxxxxxxxxxxxx
	P: xxxxxxxxxxx	G: xxxxx	T: xxxxxxxxxxx xxxxxxxxxxx	E: xxxxxxxxxxxxxxxx
	A: xxxxxxxx xxxxx xxxxxxxxxxx xxxxx	R: xxx xxxxxxxx	O: xxxxxxxxxxxxxxxx	
		S: xx		
S: xxxxxx	S: xxxx xxxxxxxxxxx xxxxxx	A: xx	A: xxx xx xxxxxxxx	S: xxxxxxxxxxxxxxxx
A: xxxx	P: xxxxxxxxxxx	G: xxxxxxxx	T: xxxxx	E: xxxxxxxxxxxxxxxx
E: xxxxxxxx	A: xxxxxxxxxxx xxxxx	R: xxx xxxxxxxx	O: xxxxxxxxxxxxxxxx	
		S: xxx		
S: xxxxxx	S: xxxx xxxxxxxxxxx xxxxxx	A: xx	A: xxx xx xxxxxxxx	S: xxxxxxxxxxxxxxxx
A: xxxx	P: xxxxxxxxxxx	G: xxxxxxxx	T: xxxxx	E: xxxxxxxxxxxxxxxx
E: xxxxxxxx	A: xxxxxxxxxxx xxxxx	R: xxx xxxxxxxx	O: xxxxxxxxxxxxxxxx	
		S: xxx		
	S: xxxxxxxx xxxxxxxxxxx xxx xxxxxxxxxxx	A: xxx	A: xxx xxxxxxxxxxx	S: xxxxxxxxxxxxxxxx
	P: xxxxxxxxxxx	G: xxxxx	T: xxxxxxxxxxx xxxxxxxxxxx	E: xxxxxxxxxxxxxxxx
	A: xxxxxxxx xxxxx xxxxxxxxxxx xxxxx	R: xxxxxxxx	O: xxxxxxxxxxxxxxxx	
		S: xx		

¹ Day is calculated as date - date of first application for dates prior to first application. Otherwise, day is calculated as date - date of first application + 1 for dates on or after first application.

Note: System Organ Class and Preferred Term map to MedDRA (Version 21.0).

SOURCE: USERNAME\SPONSOR\PROJECT\JOBNAME (DATE, TIME)

Listing sorted by Subject, Start Date, End Date, Adverse Event.

Listing 16.2.7.2.4: Serious Adverse Events
Treatment Arm
(Page xx of yy)

	S: MedDRA System Organ Class			
	P: MedDRA Preferred Term	A: In the Application Area		
S: Subject	A: Adverse Event	G: Severity	A: Action Taken with Study Drug	
A: Age/Sex	O: Occurred Prior to First Application	R: Relationship to Study Drug	T: Action Taken to Treat Event	S: Start Date (Day) ¹
E: Eval		S: Serious Event	O: Outcome	E: End Date (Day) ¹

S: xxxxxx	S: xxxx xxx xxxxxxxxxxxxxxx xxxxxx	A: xx	A: xxx xx xxxxxxxx	S: xxxxxxxxxxxxxxxxx
A: xxxx	P: xxx xxxxxxxxxxxxxxx	G: xxxx	T: xxxx	E: xxxxxxxxxxxxxxxxx
E: xxxxxxxx	A: xxxxxxxx xxx xxxxxxxxxxx xxxxx	R: xxx xxxxxxxx	O: xxxxxxxxxxxxxxxxx	
	O: xx	S: xxx		
	S: xxxxxxx xxxxxxxxxxx xxx xxxxxxxxx	A: xxx	A: xxx xxxxxxxxxxx	S: xxxxxxxxxxxxxxxxx
	P: xxxxxxxxxxx	G: xxxx	T: xxxxxxxxxxxxxxx xxxxxxxxxxx	E: xxxxxxxxxxxxxxxxx
	A: xxxxxxx xxx xxxxxxxxxxx xxxxx	R: xxx xxxxxxxx	O: xxxxxxxxxxxxxxxxx	
	O: xx	S: xxx		
S: xxxxxx	S: xxxx xxxxxxxxxxx xxxxxx	A: xx	A: xxx xx xxxxxxxx	S: xxxxxxxxxxxxxxxxx
A: xxxx	P: xxxxxxxxxxx	G: xxxxxxxx	T: xxxx	E: xxxxxxxxxxxxxxxxx
E: xxxxxxxx	A: xxxxxxxxxxx xxxxx	R: xxxxxxxx	O: xxxxxxxxxxxxxxxxx	
	O: xx	S: xxx		

¹ Day is calculated as date - date of first application for dates prior to first application. Otherwise, day is calculated as date - date of first application + 1 for dates on or after first application.

Note: System Organ Class and Preferred Term map to MedDRA (Version 21.0).

SOURCE: USERNAME\SPONSOR\PROJECT\JOBNAME (DATE, TIME)

Listing sorted by Subject, Start Date, End Date, Adverse Event.

Listing 16.2.7.2.5: Subjects Who Prematurely Discontinued Study and/or Discontinued Study Drug Due to Adverse Events
Treatment Arm
(Page xx of yy)

	S: MedDRA System Organ Class		A: In the Application Area		A: Action Taken with Study Drug	
S: Subject	P: MedDRA Preferred Term		G: Severity		T: Action Taken to Treat Event	S: Start Date (Day) ¹
A: Age/Sex	A: Adverse Event		R: Relationship to Study Drug		O: Outcome	E: End Date (Day) ¹
E: Eval	O: Occurred Prior to First Application		S: Serious Event			

S: xxxxxx	S: xxxx xxx xxxxxxxxxxxxxxx xxxxxx	A: xx	A: xxx xx xxxxxxxx	S: xxxxxxxxxxxxxxxx
A: xxxx	P: xxx xxxxxxxxxxxxxxx	G: xxxx	T: xxxx	E: xxxxxxxxxxxxxxxx
E: xxxxxxxx	A: xxxxxxxx xxx xxxxxxxxxxx xxxxx	R: xxx xxxxxxxx	O: xxxxxxxxxxxxxxxx	
	O: xx	S: xxx		
	S: xxxxxxxx xxxxxxxxxxx xxx xxxxxxxxxxx	A: xxx	A: xxx xxxxxxxxxxx	S: xxxxxxxxxxxxxxxx
	P: xxxxxxxxxxx	G: xxxx	T: xxxxxxxxxxxxxxx xxxxxxxxxxx	E: xxxxxxxxxxxxxxxx
	A: xxxxxxxx xxx xxxxxxxxxxx xxxxx	R: xxx xxxxxxxx	O: xxxxxxxxxxxxxxxx	
	O: xx	S: xxx		
S: xxxxxx	S: xxxx xxxxxxxxxxx xxxxxx	A: xx	A: xxx xx xxxxxxxx	S: xxxxxxxxxxxxxxxx
A: xxxx	P: xxxxxxxxxxx	G: xxxxxxxx	T: xxxx	E: xxxxxxxxxxxxxxxx
E: xxxxxxxx	A: xxxxxxxxxxx xxxxx	R: xxxxxxxx	O: xxxxxxxxxxxxxxxx	
	O: xx	S: xxx		

¹ Day is calculated as date - date of first application for dates prior to first application. Otherwise, day is calculated as date - date of first application + 1 for dates on or after first application.

Note: System Organ Class and Preferred Term map to MedDRA (Version 21.0).

SOURCE: USERNAME\SPONSOR\PROJECT\JOBNAME (DATE, TIME)

Listing sorted by Subject, Start Date, End Date, Adverse Event.

Listing 16.2.8.1: Urine Pregnancy Tests
Treatment Arm
(Page xx of yy)

Subject	Age/Sex	Eval	Visit	Date of Assessment	Results	Reason Test Not Done
xxxxxx	xxxx	xxxxxxxx	xxxxxxxx xxxxxxxx xxxx x xxxx x xxxx x	xxxxxxxx xxxxxxxx xxxxxxxx xxxxxxxx	xxxxxxxx xxxxxxxx xxxxxxxx xxxxxxxx	xxx xxxx
xxx	xxxx	xxxxxxxx	xxxxxxxx xxxxxxxx xxxx x xxxx x xxxx x	xxxxxxxx xxxxxxxx xxxxxxxx xxxxxxxx	xxxxxxxx xxxxxxxx xxxxxxxx xxxxxxxx	
xxx	xxxx	xxxxxxxx	xxxxxxxx xxxxxxxx xxxx x xxxx x xxxx x			xxx xxxxxxxx xxx xxxxxxxx xxx xxxxxxxx xxx xxxxxxxx xxx xxxxxxxx

SOURCE: USERNAME\SPONSOR\PROJECT\JOBNAME (DATE, TIME)

Listing sorted by Subject and Visit Number.

Listing 16.2.8.2: Physical Examination
Treatment Arm
(Page xx of yy)

Subject	Age/Sex	Eval	Visit	Date of Assessment	Body System	Exam Finding	Reason Exam Not Done
xxxxxx	xxxx	xxxxxxxx	xxxxxx	xxxxxxxx	xxxx xxxx xxxxxx xxxxxxxxxxxxxxxx xxxxxxxxxxxxxxxxxxxxxxxxxxxx xxxxxxxxxx	xxxxxx xxxxxx xxxxxx xxxxxxxxxx xxxxxxxxxxxx xxxxxx xxxxx xxx xx xxxxxxxxxx xx xxxxx xxxxxxx	
			xxxx xxxxx	xxxxxxxx	xxxx xxxx xxxxxx xxxxxxxxxxxxxxxx xxxxxxxxxxxxxxxx xxxxxxxxxxxxxxxx	xxx xxx xxx xxx xxx xxx	xxx xxxxxxxxxxx xxx xxxxxxxxxxx xxx xxxxxxxxxxx
xxxxxx	xxxx	xxxxxxxx	xxxxxx	xxxxxxxx	xxxx xxxx xxxxxx xxxxxxxxxxxxxxxx xxxxxxxxxxxxxxxxxxxxxxxxxxxx xxxxxxxxxx	xxxxxx xxxxxx xxxxxx xxxxxxxxxx xxxxxxxxxxxx xxxxxx xxxxx xxx xx xxxxxxxxxx xx xxxxx xxxxxxx	
			xxxx xxxxx	xxxxxxxx	xxxx xxxx xxxxxx xxxxxxxxxxxxxxxx xxxxxxxxxxxxxxxx xxxxxxxxxxxxxxxx	xxx xxx xxx xxx xxx xxx	xxx xxxxxxxxxxx xxx xxxxxxxxxxx xxx xxxxxxxxxxx

SOURCE: USERNAME\SPONSOR\PROJECT\JOBNAME (DATE, TIME)

Listing sorted by Subject, Visit Number, and Body System (in order presented on eCRF).

Listing 16.2.8.3: Vital Signs
Treatment Arm
(Page xx of yy)

Subject	Age/Sex	Eval	Visit	Date of Assessment	Vital Sign	Result	Units
xxxxxx	xxxx	xxxxxxxx	xxxxxxxx	xxxxxxxx	xxxxxxxx xxxxx xxxxxxxx xxxxx xxxx xxxxxx xxxxxxxxxxxxx xxxx xxxxxxxx xxxxx xxxxxxxx xxxxxxxxxxxxx xxxxxx	xx xx xxxxx xx xxx xxxxx xxx	xxxx xxxxxxxxxx xx xxxxxxxxxxxxx xxxxx x xx
			xxxx xxxxx	xxxxxxxx	xxxxxxxx xxxxx xxxxxxxx xxxxx xxxx xxxxxxxxxxxxx xxxx xxxxxxxx xxxxx xxxxxxxx xxxxxxxxxxxxx	xx xxx xxxx xxx xxx xx	xxxx xxxxxxxxxxxxx xxxxx x
xxxxxx	xxxx	xxxxxxxx	xxxxxxxx	xxxxxxxx	xxxxxxxx xxxxx xxxxxxxx xxxxx xxxx xxxxxx xxxxxxxxxxxxx xxxx xxxxxxxx xxxxx xxxxxxxx xxxxxxxxxxxxx xxxxxx	xx xx xxx xx xx xx xxx	xxxx xxxxxxxxxx xx xxxxxxxxxxxxx xxxxx x xx
			xxxx xxxxx	xxxxxxxx	xxxxxxxx xxxxx xxxxxxxx xxxxx xxxx xxxxxxxxxxxxx xxxx xxxxxxxx xxxxx xxxxxxxx xxxxxxxxxxxxx	xxx xxxx xxx xxxx xxx xxxx xxx xxxx xxx xxxx	

SOURCE: USERNAME\SPONSOR\PROJECT\JOBNAME (DATE, TIME)

Listing sorted by Subject, Visit Number, and Vital Sign (in alphabetical order).

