#### 12.5. Precautions

The following precautions are to be taken during this study:

1. Patients should avoid contact of the study product with the eyes, mouth, and lips or on any cuts or broken skin. In case of accidental exposure, the eyes should be rinsed with plenty of water.
2. The study product should not be applied to cuts, abrasions, eczematous or sunburned skin.
3. Patients should wash hands before and after applying study product.
4. Patients should allow the treated area to completely dry for at least 30 minutes after applying the study product to avoid spreading it on other areas of the face (e.g., eyes, ears, neck, etc.) and pillow cases.
5. The study product should be spread evenly in a thin layer on each area of the face (chin, left cheek, right cheek, nose, left forehead and right forehead); excessive rubbing must be avoided.
6. The study product should not be applied more than once daily and patients should not use more than the recommended amount.
7. Patients should not wash their face more than 2 or 3 times a day.
8. Facial makeup (non-medicated) may be applied according to the patient's normal daily routine (but not prior to 30 minutes after study product application).
9. Patients should not apply moisturizers, make-up, creams, lotions, powders or any topical product they do not routinely use on their face
10. Patients should not cover the treated area with a bandage (occlusive dressing) or other types of dressing after applying the study product.
11. Patients should limit sun exposure, including sunlamps (non-prescription UV light sources); avoid tanning beds/booths/parlors and sauna while using the study product.
12. Patient should use moisturizer with SPF supplied by the Sponsor or from study-approved list product and protective apparel (e.g. wide- brimmed hat) when outdoors. Patients should wait approximately 30 minutes after study product is applied on the face before applying a sunscreen. Weather extremes, such as wind or cold, may be irritating to patients receiving treatment.
13. UVA/UVB treatments are also prohibited.
14. Patients must not wear make-up to any study visits, so as not to interfere with the evaluations. If a patient comes to his/her visits with make-up on his/her face, the patient will be allowed to wash his/her face with a non-medicated cleanser and must wait at least 30 minutes before any study evaluation is made by the Principal Investigator (PI) or Sub-Investigator (Sub-I).

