8.4.4 Per-Protocol (PP) Population

All subjects in the ITT population who complete the Week 12 evaluation without noteworthy study protocol violations (i.e., any patient or investigator activity that could have possibly interfered with the therapeutic administration of the treatment or the precise evaluation of treatment efficacy) will be included in the PP population and analyzed according to the treatment group they received. The PP population will include subjects in the ITT population who do not meet any of the following criteria:

- Failed any of the inclusion/exclusion criteria;
- Have taken any interfering concomitant medications;
- Did not attend the Week 12 Visit;
- Missed more than 1 post-baseline study visit prior to Week 12;
- Have not been compliant with the dosing regimen (i.e., Patients may not miss more than five consecutive days of dosing and must take 80 to 120% of expected applications. The number of expected applications will be determined for each patient based on the length of their participation in the study);
- Out of visit window (± 4 days) at the 12-week Visit.

Subjects that discontinue from the study due to an AE related to study treatment or documented lack of treatment effect will be included in the PP population. Data for these subjects will not be imputed by multiple imputation but rather their data will be imputed with values consistent with their status as treatment failures. See Section 8.1.5 for additional detail. Prior to breaking the blind, other additional criteria may be added to the list to accommodate for unforeseen events that may occur during the conduct of the trial and result in noteworthy study protocol violations.

All efficacy analyses performed on the PP population will be according to the treatment they received.

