8.8 Safety Evaluation

8.8.1 Extent of Exposure

The extent of exposure to study drug in each treatment group will be summarized by total number of days of exposure, total number of applications, number of missed applications and number and percentage of subjects who are compliant. A subject will be considered compliant with the dosing regimen if the subject applied 80% to 120% of the expected number of applications and did not miss more than 5 consecutive applications while enrolled in the study.

Days of exposure = Date of last study application – Date of first study application + 1

The total number of applications taken is as follows:

(Date of Last Application – Date of First Application + 1) – (Number of Days marked as missed applications on the CRF) + (Number of extra applications marked on the CRF)

If a subject did apply medication on the last day, the total number of applications expected is as follows:

Date Subject End Participation – Date of Baseline +1.

If the total number of applications exceeds 89 then it will be set to 89.

If a subject did not apply medication on the last day, the total number of applications expected is as follows:

Date Subject End Participation - Date of Baseline

If the total number of applications exceeds 88 then it will be set to 88.

Compliance will be calculated as a percentage as 100 times the total number of applications taken from the first application until Week 12 divided by the total number of applications expected from first application until Week 12. Subjects who discontinue study medication before Week 12 will be considered to be 0% compliant for the number of days from discontinuing study medication until Week 12.

Compliance will not be calculated for subjects who are lost to follow-up or subjects who have unknown first or last application dates.

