
Subject	Age/Sex	Eval	Visit	Visit Date	Study Day ¹	Within Visit Window ²	Reason Screening And Baseline Occurred on Different Days	Reason for Unscheduled Visit
xxxxxx	xxxx	xxxxxxxx	xxxxxxxx	xxxxxxxx	xx	xxx		
			xxxxxxxx	xxxxxxxx	xx	xxx	xxxxxxxx xxx xx	
			xxxx x	xxxxxxxx	xx	xxx	xxxxxxxx	
			xxxx x	xxxxxxxx	xx	xxx		
			xxxx x	xxxxxxxx	xx	xxx		
			xxxx xxxxx	xxxxxxxx	xx	xxx		
xxxxxx	xxxx	xxxxxxxx	xxxxxxxx	xxxxxxxx	xx	xxx		
			xxxxxxxx	xxxxxxxx	xx	xxx		
			xxxx x	xxxxxxxx	xx	xxx		
			xxxx x	xxxxxxxx	xx	xxx		
			xxxxxxxxxxxx xxxxx xxx	xxxxxxxx	xx	xxx		xxxxxxxxxxxx
			xxxx x	xxxxxxxx	xx	xxx		
			xxxx xxxxx	xxxxxxxx	xx	xxx		
xxxxxx	xxxx	xxxxxxxx	xxxxxxxx	xxxxxxxx	xx	xxx		
			xxxxxxxx	xxxxxxxx	xx	xxx		
			xxxx x	xxx xxx	xx	xxx		xxx xxx
			xxxx x	xxx xxx	xx	xxx		xxx xxx
			xxxx x	xxxxxxxx	xx	xxx		
			xxxx xxxxx	xxxxxxxx	xx	xxx		

¹ Day is calculated as date - Baseline date for dates prior to Baseline visit. Otherwise, day is calculated as date - Baseline date + 1 for dates on or after Baseline visit.

² Determined by protocol-specified visit window for scheduled visits after Baseline.

SOURCE: USERNAME\SPONSOR\PROJECT\JOBNAME (DATE, TIME)

Listing sorted by Subject and Visit Number.

Listing 16.2.5.2: Subject Dosing Compliance
Treatment Arm
(Page xx of yy)

Subject	Age/Sex	Eval	Date of First Application	Date of Last Application	Number of Days of Exposure	Calculated ¹ Number of Applications	Amount of Study Drug Used (g)	Maximum Number of Consecutive Missed Applications	Percent Compliant	Compliant ²
xxxxxx	xxxx	xxxxxxxx	xxxxxxxxxx	xxxxxxxxxx	xx	xx	xxxx	xx	xxxxx	xxx
xxxxxx	xxxx	xxxxxxxx	xxxxxxxxxx	xxxxxxxxxx	xx	xx	xxxx	xx	xxxxx	xxx
xxxxxx	xxxx	xxxxxxxx	xxxxxxxxxx	xxxxxxxxxx	xx	xx	xxxx	xx	xxxxx	xxx
xxxxxx	xxxx	xxxxxxxx	xxxxxxxxxx	xxxxxxxxxx	xx	xx	xxxx	xx	xxxxx	xxx
xxxxxx	xxxx	xxxxxxxx	xxxxxxxxxx	xxxxxxxxxx	xx	xx	xxxx	xx	xxxxx	xxx

¹ The total number of applications was calculated using the date of first application, date of last application, and number of applied applications at a deviation.

² A subject was considered compliant with the dosing regimen if the subject did not miss more than 5 consecutive days applying and applied 80-120% of expected applications based on the length of their participation in the study.

SOURCE: USERNAME\SPONSOR\PROJECT\JOBNAME (DATE, TIME)

Listing sorted by Subject.

Listing 16.2.5.3: Subject Dosing Deviations
Treatment Arm
(Page xx of yy)

Subject	Age/Sex	Eval	Date of Dosing Deviation (Day) ¹	Number of Applications Applied

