xxxxxx	xxxx	xxxxxxx	xxxxxxxxxxxxx xxxxxxxxxxxxx	x x
xxxxxx	xxxx	xxxxxxx	xxxxxxxxxxxxx	x
xxxxxx	xxxx	xxxxxxx	xxxxxxxxxxxxx xxxxxxxxxxxxx xxxxxxxxxxxxx xxxxxxxxxxxxx xxxxxxxxxxxxx xxxxxxxxxxxxx xxxxxxxxxxxxx	x x x x x x x
xxxxxx	xxxx	xxxxxxx	xxxxxxxxxxxxx xxxxxxxxxxxxx	x x
xxxxxx	xxxx	xxxxxxx	xxxxxxxxxxxxx	x

¹ Day is calculated as date - date of first application for dates prior to first application. Otherwise, day is calculated as date - date of first application + 1 for dates on or after first application.

SOURCE: USERNAME\SPONSOR\PROJECT\JOBNAME (DATE, TIME)

Listing sorted by Subject and Date of Dosing Deviation.

Listing 16.2.5.4: Study Medication Accountability Log
 Treatment Arm
 (Page xx of yy)

Subject	Age/Sex	Eval	Kit Number	Kit Contents	Pump Identifier	Dispensing		Return		Amount Used (g)
						Date	Weight (g)	Date	Weight (g)	
xxxxxx	xxxx	xxxxxxxx	xxxx	xxxx	x	xxxxxxxxxx	xxxx	xxxxxxxxxx	xxxx	xxxx
				xxxx	x	xxxxxxxxxx	xxxx	xxxxxxxxxx	xxxx	xxxx
				xxxx	x	xxxxxxxxxx	xxxx	xxxxxxxxxx	xxxx	xxxx
				xxxx	x	xxxxxxxxxx	xxxx	xxxxxxxxxx	xxxx	xxxx
xxxxxx	xxxx	xxxxxxxx	xxxx	xxxx	x	xxxxxxxxxx	xxxx	xxxxxxxxxx	xxxx	xxxx
				xxxx	x	xxxx xxxx		xxxx xxxx		
				xxxx	x	xxxxxxxxxx	xxxx	xxxxxxxxxx	xxxx	xxxx
				xxxx	x	xxxxxxxxxx	xxxx	xxxxxxxxxx	xxxx	xxxx
xxxxxx	xxxx	xxxxxxxx	xxxx	xxxx	x	xxxxxxxxxx	xxxx	xxxxxxxxxx	xxxx	xxxx
				xxxx	x	xxxxxxxxxx	xxxx	xxxxxxxxxx	xxxx	xxxx
				xxxx	x	xxxxxxxxxx	xxxx	xxxxxxxxxx	xxx xxxx	xxxx
				xxxx	x	xxxxxxxxxx	xxxx	xxxxxxxxxx	xxxx	xxxx

SOURCE: USERNAME\SPONSOR\PROJECT\JOBNAME (DATE, TIME)

Note to programmers: Kit Contents is the treatment the kit contained.

Listing 16.2.5.5: Photography
 Treatment Arm
 (Page xx of yy)

Subject	Age/Sex	Eval	Visit	Were Photographs Taken	Date Taken
xxxxxx	xxxx	xxxxxxxx	xxxxxxxx	xxx	xxxxxxxxxx
			xxxx x	xxx	xxxxxxxxxx
			xxxx x	xx	
			xxxx x	xxx	xxxxxxxxxx
			xxxx xxxxx	xxx	xxxxxxxxxx
xxxxxx	xxxx	xxxxxxxx	xxxxxxxx	xxx	xxxxxxxxxx
			xxxx x	xxx	xxxxxxxxxx
			xxxx x	xxx	xxxxxxxxxx
			xxxx x	xxx	xxxxxxxxxx
			xxxxxxxxxxxx xxxxx xxx	xxx	xxxxxxxxxx
			xxxx xxxxx	xx	
xxxxxx	xxxx	xxxxxxxx	xxxxxxxx	xxx	xxxxxxxxxx
			xxxx x	xxx	xxxxxxxxxx
			xxxx x	xxx	xxxxxxxxxx
			xxxx x	xxx	xxxxxxxxxx
			xxxx xxxxx	xxx	xxxxxxxxxx

SOURCE: USERNAME\SPONSOR\PROJECT\JOBNAME (DATE, TIME)

Listing sorted by Subject and Visit Number

Listing 16.2.6.1: Investigator Global Assessment
 Treatment Arm
 (Page xx of yy)

Subject	Age/Sex	Eval	Visit	Date of Assessment	Evaluator Initials	Result

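### The dosing-compliance count lets an extra application offset a missed day, so a patient treated on fewer than 80% of days can pass the numeric dosing criterion for the per-protocol set

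*SAP*

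**What the plan says.** SAP 8.8.1 builds the number of applications taken from the days between first and last application, inclusive. It then subtracts and adds two CRF counts: "Number of Days marked as missed applications on the CRF) + (Number of extra applications marked on the CRF". Footnote 1 of Listing 16.2.5.2 describes its count as based on the "date of first application, date of last application, and number of applied applications at a deviation"; the operative formula is the one in 8.8.1.

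The denominator is the length of participation from Baseline, with a ceiling. For a patient who applied on the last day, "If the total number of applications exceeds 89 then it will be set to 89"; for one who did not, "If the total number of applications exceeds 88 then it will be set to 88". On the percentage itself: "Compliance will be calculated as a percentage as 100 times the total number of applications taken from the first application until Week 12". The divisor is the expected count for that same period.

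SAP 8.4.4 uses this for PP membership: "Patients may not miss more than five consecutive days of dosing and must take 80 to 120% of expected applications". Protocol 19.1.4 carries the same two limits for doses without defining the numerator. Protocol 18.5 sets a once-daily regimen, and protocol 12.5, item 6, adds: "The study product should not be applied more than once daily and patients should not use more than the recommended amount".

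**The concern.** A missed day and a second application on the same day are both departures from a once-daily regimen. In the SAP's sum they carry opposite signs and cancel, so a patient with both kinds of departure scores closer to 100% than one with misses alone. The only other numeric test, on consecutive missed days, does not see scattered misses, and neither document limits total missed days.

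Two outputs depend on the result: the supportive PP analysis of both co-primary endpoints (Table 14.2.1.3) and the compliance rate in Table 14.3.0.1. SAP 8.1.9 justifies the PP set by its lower variability in treatment response. A numeric criterion that can retain patients with substantial gaps in treatment works against that aim.

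**Working it through.** **Inputs.** From SAP 8.8.1: taken = (last date − first date + 1) − missed days + extra applications; expected = participation days, with ceilings of 89 and 88. From SAP 8.4.4: pass if taken/expected is 80–120% and no run of missed days exceeds 5. From the visit schedule: Week 12 is Day 85 ± 4.

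**The plan's own figure.** Day 85 + 4 = Day 89, so 89 applications are expected if one is made on the last day and 88 if not. Both ceilings are reproduced.

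**Pass condition with 84 expected** (for example, end of participation on Day 85, no application that day, last application on Day 84). The limits are 0.8 × 84 = 67.2 and 1.2 × 84 = 100.8, so a patient passes with 68 to 100 applications. Missed minus extra must therefore lie between −16 and +16, with no run of misses over 5.

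| Missed | Extra | Net count / expected | Days treated / expected | Numeric criterion (no run over 5) |
|---|---|---|---|---|
| 20 | 0 | 64/84 = 76.2% | 64/84 = 76.2% | fails |
| 20 | 4 | 68/84 = 81.0% | 64/84 = 76.2% | passes |
| 25 | 10 | 69/84 = 82.1% | 59/84 = 70.2% | passes |
| 0 | 20 | 104/84 = 123.8% | 84/84 = 100.0% | fails (upper limit) |

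The first two rows isolate the mechanism. The days treated are the same, and four extra applications turn a fail into a pass.

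**A larger illustration, 85 expected.** Two applications on odd days and none on even days, Days 1–85: taken = 85 − 42 + 43 = 86; 86/85 = 101.2%; longest gap 1 day; passes. Single applications on the same odd days: 85 − 42 = 43; 43/85 = 50.6%; fails. Without extras, at most 85 − 68 = 17 days can be missed, since 0.8 × 85 = 68.

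**How often it could matter.** The documents give no rates, so this rests on assumption: 84 days, independent daily misses, a stated chance of doubling on the day after a miss if that day is treated, and the 5-day rule applied.

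| Days missed | Doubling after a miss | Pass on net count | Pass on days treated |
|---|---|---|---|
| 5–10% | 5–50% | differs by under 0.5 points | – |
| 15% | 10% | 93% | 88% |
| 20% | 25% | 81% | 48% |
| 25% | 10% | 23% | 13% |
| 25% | 25% | 45% | 13% |
| 25% | 50% | 81% | 13% |

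The gap runs from nothing to very large, and the assumed behaviour decides where it falls.

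**The case against.** The strongest reply is that this is a stated definition, not a slip. Both documents express the criterion as a count of doses or applications, and a 120% ceiling has meaning only if extras are counted. That stands. A reader might infer that the 80% limit was written to remove patients treated on fewer than 80% of days, so that the formula contradicts its own purpose. Neither document says so, and neither sets a days-treated limit.

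A reader might also infer that such a patient necessarily stays in the PP set. The documents do not support that either. SAP 8.4.4 and protocol 19.1.4 also exclude noteworthy violations that could have interfered with administration of treatment, and SAP 8.1.9 and 8.3 allow further major deviations to be defined before unblinding. Sites review diaries and record missed doses, so a patient with more than 40 missed days would be conspicuous. These safeguards make exclusion possible but not certain, and they are least likely to act on the milder 20-missed, 4-extra patient. They also leave the printed compliance rate as it is.

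Nor is the information hidden. Table 14.3.0.1 has a line for missed applications, and Listing 16.2.5.3 gives the number applied on each deviation date. The table has no line for extra applications, however, so the offsetting cannot be seen in the summary. Weighed product would not show it, because skipping and then doubling uses about the same total.

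**Conclusion.** The point holds for the numeric criterion. Under SAP 8.8.1 and 8.4.4, a patient with scattered misses (no run over 5) can be classed compliant while treated on fewer than 80% of days: 76.2% of days in the mild example and 50.6% in the alternate-day one. That patient passes the dosing criterion for PP, and exclusion then depends on blinded judgment. Wherever the pattern occurs, the compliance rate in Table 14.3.0.1 is higher than a days-treated rate would be.

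The reach is limited. The ITT analyses of the co-primary and secondary endpoints are unaffected; only supportive PP and exposure output is involved. The worked examples rest on the formulas alone. Frequency rests entirely on assumption: negligible if about 10% of days or fewer are missed, large if 25% are missed and doubling is frequent. It is worth correcting as a cheap improvement to a pre-specified rule, and it does not threaten the trial's conclusions.

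**What to change.** Before unblinding:

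- In SAP 8.8.1 and 8.4.4, apply the 80% lower limit to days with at least one application divided by expected days, so that each day counts at most once. Apply the 120% upper limit to total applications. Keep the consecutive-miss rule as it is.
- Add a line for extra applications to Table 14.3.0.1, and align the footnotes that restate the rule (Tables 14.0.2.1 and 14.3.0.1, Listing 16.2.5.2).
- Record the departure from the single 80–120% criterion of protocol 19.1.4 in SAP section 10.
- Reconcile the compliance rule with the once-daily text in protocol 12.5 and 18.5. This concerns how applications are counted for analysis; no change to dosing is proposed.

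The cost is a few sentences of SAP text and a small programming change. No new data are needed, because Listing 16.2.5.3 already holds the number of applications on each deviation date. The downside is that the PP set and the printed compliance rate may be slightly smaller.
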